Descriptive statistics will be provided by treatment group/country and by all for all of the endpoints, including primary and secondary ones. Frequency table will be provided for categorical data, while mean, standard deviation, maximum, minimum, median, inter-quartile range (IQR), and 95% two-sided confidence interval will be calculated for continuous measurements.

AEs and SAEs will be reported by treatment group/country and physiological systems as appropriate. The incidence of treatment-related AEs and SAEs between treatments will be analyzed by Cochran-Mantel-Haenszel test (CMH) test.

Incidence of AEs and SAEs will be analyzed by CMH test. Changes in physical examinations will be displayed for each individual system. Net changes from pre-treatment laboratory test results and vital signs will be analyzed by descriptive statistics.

Healing time from DSW creation to 100% re-epithelialization will be estimated by using Kaplan-Meier methods and compared between groups by using log-rank test. The healing time is defined as from DSW creation to the first 100% re-epithelialization with confirmation for at least 10 days apart, observed by the investigator and the first additional evaluator.

If the first 100% re-epithelialization is observed at any visit by Day 28 with confirmation for at least 10 days apart, the healing time is noted as the duration from the day of DSW creation to the day of the first 100% re-epithelialization. The fulfilling of the visits and/or follow-ups after the 100% re-epithelialization day will not be taken into account to determine the healing time. If the 100% re-epithelialization is not observed by Day 28 visit, the healing time will be censored on day of the last visit up to Day 28 visit. If the 100% re-epithelialization is observed by Day 28 visit but no confirmation is made, the healing time will be censored on day of the last visit up to Day 28 visit. The censoring rules will be applied immediately once patients leave the study regardless the participation and/or completion of the long-term (360 days) follow-ups.

If patient develops grade 2 or above SAEs and should exit the study prematurely before Day 14, he/she should be excluded from the primary efficacy analysis, because early censor will result in under estimation of the healing time while treatment group (TWB-103+TegadermTM) is prone to have higher risk of developing treatment related SAE.

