7.4 The end of treatment visit

(Visit 6: Day 14 days ± 2 days)

- Perform physical examinations
- Obtain vital signs
- Obtain blood samples for hemogram and biochemical tests
- Pain questionnaire
- Wound assessment
- Apply Tegaderm™, Vaseline Gauze or Non-Stick Gauze (if not 100% re-epithelialization, for both treatment and control group)
- Dispense Tegaderm™, Vaseline Gauze or Non-Stick Gauze to patients
- Return unused Tegaderm™
- Record adverse events

- Record concomitant treatments

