7.5 Follow-up visits

7.5.1 Visit 7: Day 28 ± 3 days

- Perform physical examinations
- Obtain vital signs
- Obtain blood samples for hemogram and biochemical tests
- Obtain blood samples for PRA test
- Pain questionnaire
- Wound assessment
- Apply Tegaderm™, Vaseline Gauze or Non-Stick Gauze (if not 100% re-epithelialization, for both treatment and control group)
- Dispense Tegaderm™, Vaseline Gauze or Non-Stick Gauze to patients (only for patients who have Day 42 Visit)
- Return unused Tegaderm™, Vaseline Gauze or Non-Stick Gauze
- Record adverse events
- Record concomitant treatments

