7.5.2 Visit 8: Day 42 ± 3 days

(Only scheduled when the wound closure is not completed by Day14 but is observed on Day 28)

- Perform physical examinations
- Obtain vital signs

- Obtain blood samples for hemogram and biochemical tests
- Pain questionnaire
- Wound assessment
- Return unused Tegaderm™, Vaseline Gauze or Non-Stick Gauze
- Record adverse events
- Record concomitant treatments

7.5.3 Visit 9~12 (90, 180, 270, 360 days ± 14 days after Visit 7 (if no visit 8) or Visit 8)

- Perform physical examinations
- Obtain vital signs
- Pain questionnaire
- Wound assessment (scar assessment, skin texture and any altered sensations, see details in section 6.11)
- Record adverse events (only TWB-103/placebo-relative and DSWs-relative adverse events will be recorded)
- Exit of study (Visit 12)

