10.2.2 Analysis methods

For all assessments, the baseline will be defined as the most recently available data before the administration of 1st dose treatment.

Descriptive statistics will be provided by treatment group/country and by all for all of the endpoints, including primary and secondary ones. Frequency table will be provided for categorical data, while mean, standard deviation, maximum, minimum, median, inter-quartile range (IQR), and 95% two-sided confidence interval will be calculated for continuous measurements.

AEs and SAEs will be reported by treatment group/country and physiological systems as appropriate. The incidence of treatment-related AEs and SAEs between treatments will be analyzed by Cochran-Mantel-Haenszel test (CMH) test.

Incidence of AEs and SAEs will be analyzed by CMH test. Changes in physical examinations will be displayed for each individual system. Net changes from pre-treatment laboratory test results and vital signs will be analyzed by descriptive statistics.

Healing time from DSW creation to 100% re-epithelialization will be estimated by using Kaplan-Meier methods and compared between groups by using log-rank test. The healing time is defined as from DSW creation to the first 100% re-epithelialization with confirmation for at least 10 days apart, observed by the investigator and the first additional evaluator.

If the first 100% re-epithelialization is observed at any visit by Day 28 with confirmation for at least 10 days apart, the healing time is noted as the duration from the Day of DSW creation to the day of the first 100% re-epithelialization. The fulfilling of the visits and/or follow-ups after the 100% re-epithelialization date will not be taken into account to determine the healing time. If the 100% re-epithelialization is not observed by Day 28 visit, the healing time will be censored on day of the last visit up to Day 28 visit. If the 100% re-epithelialization is observed by Day 28 visit but no confirmation is made, the healing time will be censored on day of the last visit up to Day 28 visit. The censoring rules will be applied immediately once patients leave the study regardless the participation and/or completion of the long-term (360 days) follow-ups.

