If patient develops grade 2 or above SAEs and should exit the study prematurely before Day 14, he/she should be excluded from the primary efficacy analysis, because early censor will result in under estimation of the healing time while treatment group (TWB-103+TegadermTM) is prone to have higher risk of developing treatment related SAE.

In the cases of TWB-103/placebo discontinuation due to allergic reaction or infection, wound assessments performed after onset of allergic reaction or infection will be excluded from statistical analysis.

Healing rates (complete wound closure) of patients at Days 7, 10 and 14 after DSW creation will be analyzed by CMH test. Healing percentage of wounds (ratio of healing and original areas) at Days 7, 10 and 14 after DSW creation will be analyzed by Analysis of variance (ANOVA) model with treatment group and country as factor. Score on short-form McGill pain questionnaire will be analyzed by using Analysis of covariance (ANCOVA) model with treatment group and country as factor and baseline characteristics as covariate. Vancouver Scar Scale will be analyzed by Wilcoxon ranked sum test. The score in each category (pigmentation, vascularity, pliability and height) and the sum score of all category in Vancouver Scar Scale will be analyzed.

All treatment group comparisons will be conducted with significance level of 0.05, using 2-tailed tests.

Demographics and baseline characteristics will be summarized for each group/country by using descriptive statistics.

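### Visit 7 outcomes are dated to the actual day within Day 25–31, so the end of the Kaplan-Meier curve overstates healing and the log-rank test loses some power

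*Combined protocol and SAP*

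**What the plan says.** The primary efficacy endpoint is healing time, "estimated by using Kaplan-Meier methods and compared between groups by using log-rank test" (section 10.2.2). For a confirmed closure, "the healing time is noted as the duration from the Day of DSW creation to the day of the first 100% re-epithelialization", which in practice is the day of the visit at which it is first seen. For a wound not closed, the same section says that if closure is "not observed by Day 28 visit, the healing time will be censored on day of the last visit up to Day 28 visit"; the synopsis repeats this rule. A closure that is not confirmed is censored in the same way.

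The section 7 headings give the windows: "Visit 6: Day 14 days ± 2 days" and then "Visit 7: Day 28 ± 3 days". Visit 8 follows only for wounds first found closed at Visit 7: "Only scheduled when the wound closure is not completed by Day14 but is observed on Day 28". No section maps visits to nominal days, sets a common censoring day or specifies an interval-censored method.

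**The concern.** A wound found open at Visit 7 has a final outcome for this endpoint. It cannot become an event later, because only closures seen by the Day 28 visit count. Kaplan-Meier nevertheless treats it as a patient lost while still at risk, and passes its weight to patients seen later in the window. If it is seen on Day 25 and another patient's closure is recorded on Day 29, the open wound is no longer in the risk set when that closure is counted. The order of days within the window reflects only when appointments were made.

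Two things are at stake in the primary analysis. The right-hand end of the published curve can show more healing than was observed. And the log-rank test ranks Visit 7 patients partly by appointment date, which costs power in a trial of about 36 patients. The plan already recognises in 10.2.2 that early censoring can distort this endpoint, since it excludes certain early exits for that reason, but it has no safeguard for this case.

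**Working it through.** **Inputs from the protocol.** Two-sided 0.05 level; Kaplan-Meier and log-rank; Visits 3 to 7 on Days 3±1, 7±1, 10±1, 14±2 and 28±3; about 36 recruited at 1:1, so 36/2 = 18 per arm, of whom 15 per arm are to be evaluable. The sample size is stated not to rest on a power calculation, so there is no planned power to reproduce. The only guide to healing is section 1.1, which expects closure in 7 to 21 days.

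**Assumptions, not in the documents.** Lognormal healing times, visit days uniform within their windows, and every first closure confirmed.

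**Step 1: the mechanism, by hand.** Take 18 patients, 9 closed by Day 14. At Visit 7, two wounds are open (Days 25 and 26) and seven are closed (Days 27, 28, 28, 28, 29, 30, 31). Observed share closed: 16/18 = 88.9%.
- After Day 14, S = 9/18 = 0.5, with 9 at risk. The two open wounds are censored, leaving 7.
- S(28) = 0.5 × 6/7 × 3/6 = 0.214, so 1−KM = 78.6%.
- S(31) = 0.214 × 2/3 × 1/2 × 0/1 = 0, so 1−KM = 100%.
- With all nine Visit 7 outcomes on Day 28 and events first: S = 0.5 × 2/9 = 0.111, so 1−KM = 88.9%, the observed share.

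This case puts the open wounds first on purpose. The curve is too low in mid-window and too high at the end.

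**Step 2: averaged over visit order.** Take 15 patients, 8 closed by Visit 6, and 4 of the other 7 found closed at Visit 7. Observed share: 12/15 = 80%. Over all equally likely orders without ties, the expected final 1−KM is 94%. It equals 100% whenever the last patient seen is a closure: 4/7 = 57% of orders.

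**Step 3: size of the curve bias** (simulated control arm, 18 per arm).

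| Closed by Visit 7 | Bias of final 1−KM |
|---|---|
| 99% | 0.7 points |
| 97% | 2.4 points |
| 94% | 5.4 points |
| 86% | 11.7 points |

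**Step 4: log-rank power, with the two causes separated** (18 per arm). The middle dating changes only the censoring, keeping open wounds at risk to Day 31. The last puts all Visit 7 outcomes on Day 28.

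| Medians in days, control/treated (log-SD) | As written | Open wounds censored Day 31 | All Visit 7 on Day 28 | Total loss | Part due to censoring |
|---|---|---|---|---|---|
| 12/9.5 (0.28) | 0.503 | 0.503 | 0.544 | 4.1 | 0.0 |
| 13/10 (0.25) | 0.655 | 0.657 | 0.728 | 7.3 | 0.2 |
| 14/11 (0.35) | 0.325 | 0.344 | 0.404 | 7.9 | 1.9 |
| 16/12 (0.35) | 0.398 | 0.438 | 0.528 | 13.0 | 4.0 |
| 24/17 (0.40) | 0.380 | 0.518 | 0.584 | 20.4 | 13.8 |

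Losses are in percentage points: column 4 minus column 2, and column 3 minus column 2. Repeat runs agree to about 2 points. At 18/14 (0.40), power is 0.25 as written against 0.37 on a common day. Under the null, rejection is 0.054 as written and 0.045 with common-day dating.

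**Step 5: visit spread.** With 80% of visits exactly on the nominal day, the power loss falls to about 3–9 points (about 6 at medians 18/14). With all visits on the nominal day, the datings coincide and both effects vanish.

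**The case against.** The strongest reply is that little here touches what the trial will conclude. The endpoint is healing time. The planned healing rates are at Days 7, 10 and 14 and are unaffected, and no Kaplan-Meier proportion at the end of the curve is specified. Medians reached before Day 25 do not move. The sample size is declared arbitrary, so no planned power is breached. If wounds heal in the 7 to 21 days expected in section 1.1, very few are open at Visit 7. All of this stands, and it limits the weight of the point.

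It does not remove it. The plan estimates the whole curve, and its end will be read as the share healed. Even in the 14/11 case, where about 97% of controls are closed by Visit 7, the test loses about 8 points of power for no gain.

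A reader might infer that the censoring rule is what weakens the test. Step 4 does not support that. Correcting only the censoring recovers a minority of the loss except in the slowest case; the rest comes from scattering Visit 7 closures over seven days. In the faster cases, ignoring Visit 7 altogether gives nearly the same power as the common-day fix (0.388 against 0.404 at 14/11), so what is removed there is mainly appointment-order noise.

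**Conclusion.** The point holds. Sections 10.2.2, 7.5.1 and 7.5.2 together treat one final look as outcomes on up to seven different days.

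- **Curve:** the end overstates the share healed by about 0–2 points if 97% or more of wounds are closed by Visit 7, which fits section 1.1, and by about 5–12 points if 86–94% are.
- **Power:** the loss against common-day dating is about 7–13 points in plausible cases (about 4 in the fastest case tried) and about 20 with slow healing. The censoring rule alone accounts for about 0–5 points, or about 14 at medians 24/17, where many wounds stay open.

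These sizes rest on lognormal healing, uniform visit days and 18 per arm, none of which the documents give except the numbers recruited. They shrink if most Visit 7 dates fall on Day 28.

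A reader might also infer a raised false-positive rate or a biased median. Neither follows: type I error stays near 5%, and a median reached before Day 25 is unchanged.

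**What to change.** Add to section 10.2.2 and the synopsis: for the Kaplan-Meier estimate and the log-rank test, all Visit 7 outcomes, whether closed or open and censored, are assigned nominal Day 28, with events ordered before censorings; assessments made at an early withdrawal keep their actual date. Keep the actual-day analysis as a sensitivity analysis.

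Censoring open wounds at Day 31 instead would also correct the curve, but would recover only part of the power. Earlier visits need no change for this purpose, because a wound found open there stays at risk.

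The cost is one prespecified rule and no new data or visits. The small downside is that Visit 7 times are reported to the visit and not to the day.

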11. When patients are withdrawn from the study by Day 28, they are required to finish all assessments of Day 28, except the application and dispensation of TegadermTM. The unused TegadermTM should be returned if received from the previous visit. For patients who have initially scheduled Day 42 visit but make the decision between Day 28 to Day 42 to withdraw from the study, he/she should be encouraged to complete assessments planned for Day 42 visit at the earliest date convenient for the patients. If patients have entered the long-term follow-up period (i.e. after Day 28 or Day 42 if scheduled) and the decision of withdrawal is confirmed, effort must be made to understand and record the reason of withdrawal.
12. In case patients achieve 100% re-epithelialization before or at Day 10, patients will finish up the assessments on the day with 100% re-epithelialization. This day of 100% re-epithelialization will be the end of treatment and the remaining scheduled treatment visits, if applicable, will be dismissed.
13. When patients experience > Grade 2 skin allergic reaction or > Grade 2 systemic allergic reaction related to the product/placebo or develop infection that the continuation of TWB-103/placebo is considered inappropriate at the investigator's discretion, patients should finish the scheduled assessments (except that application of TWB-103/placebo is stopped; that the application and dispensation of TegadermTM will be at the investigator's discretion; and that the return of TegadermTM will be asked if applicable) and will continue the remaining visits (application of TWB-103 or placebo will be stopped if planned originally).
14. When unscheduled visits are requested, patients should finish the assessments of Day 14 (except that the completion of hemogram and serum biochemistry as well as the application and dispensation of TegadermTM will be at the investigator's discretion; and that the return of TegadermTM is not required) during the unscheduled visit. The option to choose Vaseline Gauze or Non-Stick Gauze such as silastic foam dressings only can be selected on or after Day 14.
15. When the first 100% re-epithelialization is not observed by Day 28, the DSWs will be followed till 100% re-epithelialization.

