In Phase I proportion, eligible patients will be recruited sequentially with one week staggering in the initiation of study treatment. Eligible patients will also be randomized into 1:1 ratio into one of Treatment (TWB-103+Tegaderm™) and Control (placebo+Tegaderm™) groups. Phase I plan to recruit 3 evaluable TWB-103+Tegaderm™ treated and 3 evaluable placebo+Tegaderm™ treated patients. Patients in phase I are considered as evaluable when (1) he/she receives at least one dose and has follow-up evaluation at least 14 days after first dose or (2) he/she receives at least one dose and has early withdrawn due to safety reasons before Day 28. When all of those 6 evaluable patients complete the planned treatment period (14 days or till first 100% re-epithelialization, which comes first), the recruitment of patients will be temporarily stopped for 14 days for safety observation. The safety data of TWB-103 before and on Day 28 Visit will be reviewed by the sponsor and the principal investigator. If no safety issue of TWB-103 is decided, the study will enter Phase II portion and eligible patients will be randomized into 1:1 ratio into one of Treatment and Control groups.

Each patient will have treatment for up to 14 days or to the day of 100% re-epithelialization, whichever comes first. Patients assigned to the Treatment Group will receive TWB-103 add-on Tegaderm™ till 100% re-epithelialization or up to 10 days,

whichever comes first and will receive Tegaderm™ alone from Day 10 to Day 14 if re-epithelialization can not be attained by Day 10. Patients assigned to the Control Group will receive placebo+Tegaderm™ till 100% re-epithelialization or up to 10 days, whichever comes first and will receive Tegaderm™ alone from Day 10 to Day 14 if re-epithelialization can not be attained by Day 10. Patients from either group (treatment or control) will have application of Tegaderm™ alone up to Day 28 if 100% re-epithelialization of DSWs is not observed on Day 14 (end of treatment).

Patients will be required to attend scheduled visits at Screening, Day 0 (treatment start day), Day 3, Day 7, Day 10, Day 14 (end of treatment). In case patients achieve 100% re-epithelialization before or at Day 10, patients will finish up the assessments on the day with 100% re-epithelialization. This day of 100% re-epithelialization will be the end of treatment and the remaining scheduled treatment visits, if applicable, will be dismissed.

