6.11 Wound assessment

The wound assessment will be measured at all scheduled visits except the Screening Visit.

From Visit 2 (Day 0) to Visit 8 (Day 42), the investigator will determine the end of treatment based on the healing progress. Wound healing will be assessed based on the wound observation by the investigator and an additional evaluator. An additional evaluator who is not aware of the treatment given will evaluate based on photos of the wound. The additional evaluator will receive photos of the wound from CRO and will return the assessment to CRO. A second additional evaluator, who is also blinded, will

be requested when the discrepancy occurs between investigator and the first additional evaluator in the determination of 100% re-epithelialization.

The photos of wound will be taken under the following guidelines.

- (a) Cameras and rulers with the same brand and model will be used throughout the study.
- (b) The study staff who are trained will be in charge of taking photos following the guidelines for each study center.
- (c) Two different photos will be taken for each wound at each visit: one for the calculation of wound healing and the other as the reference of the wound location relative to the body part.
- (d) The wound area shown in the photo specific for calculation purpose, along with the provided ruler, should have sufficient size and quality for evaluation.
- (e) Images will be processed by the software, Image J.
- (f) The investigator and evaluator(s) will select the boundary of said wound in the photo manually and by the wand tool in Image J.
- (g) Calculate the wound size by Image J based on the area selected.
- (h) The healing percentage of wounds will be calculated by the ratio of healing area and original area (Day 0).

Complete wound closure is defined as skin 100% re-epithelialization without drainage or dressing requirements. Wound closure should be re-confirmed on Day 28 when the complete wound closure occurs by Day 14, or on Day 42 in the case that complete wound closure occurs at some point between Day 14 and Day 28.

During the 360 days of follow-up (Visit 9~12), recording of 100% re-epithelialization and the area of target wound are not required. Instead, potential long-term adverse

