10.2 Statistical and Analytical Plans

10.2.1 Analysis Population

Two populations will be introduced for statistical analysis:

Intent-to-treat (ITT) population:

- Patients randomized
- Patients ever treated by at least one dose of trial medication
- Patients with any post-treatment evaluation

Per-protocol (PP) population:

- Dosed with planned dosing regimen of investigational product
- With efficacy endpoint measurement at wound assessment (with first 100% re-epithelialization or complete Day 14 visit evaluation)
- Fulfilling all inclusion and exclusion criteria
- Without taking prohibited medication

Since the dosing regimen designed in Phase I are exactly those designed for Phase II, and the procedures/schedules of assessment that patients receive are

identical in both phases, the data collected in Phase I portion will be combined with those in the Phase II portion for statistical analysis.

Primary endpoints and secondary efficacy endpoints in Phase I/II will be analyzed on ITT and PP population. Non-primary safety endpoints, demographics and baseline characteristics will be analyzed on ITT population. Conclusion of primary endpoint in Phase I will be made based on ITT population analysis results and that in Phase II will be made according to the result of ITT population analysis.

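### A closure whose re-confirmation visit is missed is censored like one found open at the check; for a patient healed by Day 14 this can mean censoring on the healing day, which biases the Kaplan-Meier healing curve towards slower healing.

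*Combined protocol and SAP*

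**What the plan says.** The primary efficacy endpoint is time from wound creation to first 100% re-epithelialization, confirmed at least 10 days later and assessed by the investigator (section 2.2.1). It is analysed by Kaplan-Meier and log-rank (section 10.2.2).

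- **Event.** "If the first 100% re-epithelialization is observed at any visit by Day 28 with confirmation for at least 10 days apart", the healing time runs to the day of first closure (section 10.2.2).
- **No confirmation.** If closure "is observed by Day 28 visit but no confirmation is made, the healing time will be censored on day of the last visit" up to the Day 28 visit, there is no event (section 10.2.2).
- **Where confirmation happens.** "Wound closure should be re-confirmed on Day 28 when the complete wound closure occurs by Day 14" (section 6.11). Closure between Day 14 and Day 28 is re-checked on Day 42.
- **Visits in between.** After closure at or before Day 10, "the remaining scheduled treatment visits, if applicable, will be dismissed" (section 4). Nothing is scheduled between Day 14 and Day 28.
- **Later visits.** At Visits 9-12, "recording of 100% re-epithelialization and the area of target wound are not required" (section 6.11). Section 10.2.2 adds that the censoring rules apply whether or not the long-term follow-up is attended.
- **Missing data.** Section 10.2.5 rules out imputation, and section 10.2 names no sensitivity analysis.

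**The concern.** The no-confirmation rule covers two different facts. In one, the patient attended and the wound had reopened; censoring at Day 28 then follows from the endpoint definition. In the other, nobody looked. The rule turns that second patient from an event into a censored observation, and the visit schedule usually puts the censoring time on the healing day itself.

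Kaplan-Meier and the log-rank test assume that a patient censored at a given time has the same prospects as those still at risk. Here the censored patient has just been seen to be healed, so the assumption fails by construction. With about 15 evaluable patients per arm, two or three lost events can visibly move the primary result.

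**Working it through.** **No plan figure to reproduce.** The 30 evaluable patients are described as an arbitrary choice (section 10.1). No power, effect size, healing rate or missed-visit rate is stated. The healing curves and missed shares below are therefore assumptions.

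**Step 1: the censoring day.** Closure is recorded at Day 7, 10 or 14, Day 28 is missed, and there is no other visit. The last visit up to Day 28 is then the closure visit, so the patient is censored at Day 7, 10 or 14. A patient who first closes on Day 28 and misses Day 42 is censored at Day 28, again the closure day.

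**Step 2: the effect on the curve.** Let p be the share first closing at a visit, R the share not closed before it, and m the share of closures by Day 14 whose check is missed. A patient censored at a tied time still counts as at risk, and leaves the risk set afterwards just as an event would. So R is unchanged and the estimated hazard is (1 - m) × p / R. The unhealed estimate is the product of 1 minus these hazards, so for m above 0 it can only be too high.

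**Step 3: a 15-patient arm (assumed counts).** Closures are 2, 4, 5 and 3 at Days 7, 10, 14 and 28, with 1 not healed.
- All confirmed, unhealed at Day 14: 13/15 × 9/13 × 4/9 = 26.7%.
- One Day 10 and one Day 14 healer miss Day 28: 13/15 × 10/13 × 5/9 = 37.0%.

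**Step 4: two arms, 20% missed in each.** Assumed true closure by Days 7/10/14/28 is 10/40/75/95% for TWB-103 and 3/20/50/85% for placebo.

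| Visit | TWB-103 p/R | × 0.8 | Unhealed | Placebo p/R | × 0.8 | Unhealed |
|---|---|---|---|---|---|---|
| Day 7 | 0.100 | 0.080 | 0.920 | 0.030 | 0.024 | 0.976 |
| Day 10 | 0.30/0.90 = 0.333 | 0.267 | 0.675 | 0.17/0.97 = 0.175 | 0.140 | 0.839 |
| Day 14 | 0.35/0.60 = 0.583 | 0.467 | 0.360 | 0.30/0.80 = 0.375 | 0.300 | 0.587 |

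Day 14 closure reads 64% v 41% instead of 75% v 50%.

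**Step 5: power with equal missed rates.** Log-rank, two-sided 0.05, 15 per arm, 20,000 simulated trials per setting on the Step 4 curves:

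| Missed in both arms | 0% | 10% | 20% | 30% |
|---|---|---|---|---|
| Power | 35% | 31% | 27% | 24% |

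A second set of assumed curves (control unhealed 90/65/35/5% at Days 7/10/14/28, hazard ratio 2) gives 37%, 32%, 28% and 24%. Under the null with equal missed rates, its rejection rate stays at 4.9-5.3%.

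**Step 6: unequal missed rates, identical true curves.** Both arms follow the placebo curve, with 30% v 10% missed. Unhealed at Day 14:
- 30% missed: (1 - 0.021) × (1 - 0.123) × (1 - 0.2625) = 0.633, so closure reads 37%.
- 10% missed: (1 - 0.027) × (1 - 0.158) × (1 - 0.3375) = 0.543, so closure reads 46%.

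The simulated type I error is about 7%, and 5.4% at 10% v 0%. On the second set of curves it is about 8% at 20% v 0% and 13% at 30% v 0%.

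**The case against.** The strongest reply is that the comparison between arms may be untouched. A reader might infer that the faster arm is penalised because it loses more events: at 20% missed, 15 × 0.75 × 0.2 = 2.25 against 15 × 0.50 × 0.2 = 1.5 by Day 14. The documents do not support that inference. With equal missed rates, every hazard up to Day 14 shrinks by the same factor in both arms, so their ratio is preserved and the test keeps its size. This objection stands; what remains is slower-looking curves and lost power.

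Nor do the documents show that missed checks would differ by arm. Patients and investigators are blinded (section 4.2), and no missed-visit rate is given. Between-arm bias is a possibility, not a finding.

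Other visits can also intervene. Patients withdrawn before Day 28 must complete the Day 28 assessments (section 3.4), and unscheduled visits repeat the Day 14 assessments (section 4.3.4). Either can move the censoring day later, or confirm closure if at least 10 days have passed. So censoring on the healing day is not universal. Neither provision covers a patient who simply misses Day 28 or is lost to follow-up.

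A reader might look to Visits 9-12 for confirmation, since recording closure there is not required rather than barred. But Visit 9 falls near Day 28 + 90 = 118, while section 1.1 expects spontaneous closure in 7 to 21 days. A wound that had reopened by Day 28 would probably be closed by then. Someone who skipped the check would be credited, while someone who attended with the same reopened wound would be censored.

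A reader might also fault the per-protocol criterion, "with first 100% re-epithelialization or complete Day 14 visit evaluation" (section 10.2.1), for accepting unconfirmed closure. Tightening it would select patients on attendance after healing and change the evaluable count that sets the recruitment target. The conclusion rests on ITT in any case.

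Finally, the secondary healing rates at Days 7, 10 and 14 state no re-confirmation requirement, so they should keep these closures. That is useful, but it does not repair the primary analysis.

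**Conclusion.** The point holds in a limited form. Section 10.2.2 merges failed and missed confirmation, and the schedule then allows a healed patient to be censored at the visit where healing was recorded. The mechanism and its direction follow from the document's own rules: any such case makes that arm's Kaplan-Meier healing look slower.

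The size rests entirely on assumed healing curves and missed shares. On those, 10-30% missed in both arms costs roughly 4 to 11 points of power from a base of about 35%, and 20% missed lowers the Day 14 closure reading by 11 points (TWB-103) and 9 points (placebo). A spurious difference between arms needs unequal missed rates. At 30% v 10% it would be about 9 points at Day 14, with type I error near 7%. The documents do not show that the comparison will be biased, only that the plan has no way to detect or bound such bias.

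**What to change.** In section 10.2.2, split the no-confirmation rule:

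- **(a) Wound found open at re-confirmation:** censor as now.
- **(b) Re-confirmation visit missed,** with no other wound assessment at least 10 days after closure and up to the end of the Day 28 window (Day 31), or of the Day 42 window (Day 45) for Day 28 healers: identify as a separate category.

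Pre-specify an ITT sensitivity analysis of the primary endpoint that counts (b) as events on the first-closure day, described as an alternative event definition because section 10.2.5 excludes imputation. Report missed and failed confirmations by arm.

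The new wording should also place one edge case. The windows allow closure on Day 14 + 2 = 16 and a check on Day 28 - 3 = 25, only 9 days apart, so an attended check can fall short of the 10-day requirement.

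Do not use Visits 9-12 as confirmation in the primary analysis, and leave the per-protocol definition unchanged.

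The cost is a few lines of SAP text, one further Kaplan-Meier and log-rank run, and one small table. No visit or data item is added. The downside is that the sensitivity analysis credits a few closures that were never re-checked, so it should be read beside the primary result, not in place of it.
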